7.7.3.2. DOCR, DOCRh, DOR, and DOCRi

DOCR is defined, for subjects who achieved CR, as the time from the first occurrence of CR to confirmed relapse or death due to any cause.

$$\text{DOCR (months)} = (\text{date of event or censoring} - \text{first date of CR} + 1) / 30.4375$$

DOCRh is defined, for subjects who achieved CR or CRh, as the time from the first occurrence of CR or CRh to confirmed relapse or death due to any cause.

$$\text{DOCRh (months)} = (\text{date of event or censoring} - \text{first date of CRh} + 1) / 30.4375$$

DOR is defined, for subjects who achieved CR, CRi (including CRp), PR, or MLFS, as the time from the first response to confirmed relapse, disease progression, or death due to any cause.

$$\text{DOR (months)} = (\text{date of event or censoring} - \text{first date of response} + 1) / 30.4375$$

DOCRi is defined, for subjects who achieved CR or CRi (including CRp), as the time from the first occurrence of CR or CRi (including CRp) to confirmed relapse or death due to any cause.

$$\text{DOCRi (months)} = (\text{date of event or censoring} - \text{first date of CR or CRi} + 1) / 30.4375$$

The outcome (event or censor), type of event and the date of event or censoring to be considered for the analysis of DOCR, DOCRh, DOR, and DOCRI are presented in [Table 8](#).

Table 8: Outcome and Event or Censoring Dates for DOCR, DOCRh, DOR, and DOCRI

Scenario	Date of event/censoring	Event (event type)/ Censored
Relapse/progression ^a	Date of relapse/progression	Event (relapse/progression)
Death (no relapse/progression)	Date of death	Event (death)
Start subsequent anticancer therapy (prior to relapse/progression or no relapse/progression)	Date of the last adequate disease assessment documenting no relapse/progression prior to start of subsequent anticancer therapy or missed disease assessments	Censored
Relapse/progression or death after two or more missing or inadequate disease assessments		Censored
Neither relapse/progression nor death		Censored

^aProgression only applies to the calculation of DOR, for which subjects with a BOR of PR may experience disease progression afterwards.

Frequency of subject with each event type and censoring reasons will be presented by treatment arm. Reasons for censoring will be summarized according to the categories in [Table 9](#) following the hierarchy shown.

Table 9: Censoring Reasons and Hierarchy for DOCR, DOCRh, DOR, and DOCRI

Hierarchy	Condition	Censoring Reason
1	Start subsequent anticancer therapy	Start subsequent anticancer therapy
2	Experience relapse/progression or die after two or more missing or inadequate disease assessments	Relapse/progression/death documented after two or more missing disease assessments
3	No relapse/progression or death, lost to follow-up	Lost to follow-up
4	No relapse/progression or death, withdrawal by subject from the study	Withdrawal by subject
5	No relapse/progression or death, ongoing in study	Ongoing without relapse/progression or death

^aProgression only applies to the calculation of DOR, for which subjects with a BOR of PR may experience disease progression afterwards.

Kaplan-Meier estimates (product-limit estimates) will be presented by treatment arm together with a summary of associated statistics including the median DOCR, DOCRh, DOR, and DOCRI time with 2-sided 95% CIs. In particular, the DOCR, DOCRh, DOR, and DOCRI rates at 3, 6, 9, 12, 18, 24 and 36 months will be estimated with corresponding

2-sided 95% CIs. The CIs for the median will be calculated according to Brookmeyer and Crowley and the CIs for the survival function estimates at the time points defined above will be derived using the log-log transformation (conftype=loglog default option in SAS PROC LIFETEST) with back transformation to a CI on the untransformed scale. The estimate of the SE will be computed using Greenwood's formula.

DOCR, DOCRh, DOR, and DOCRI will be displayed graphically and analyzed using Kaplan-Meier methodology. If the number of subjects with responses is small, the Kaplan-Meier method may not provide reliable estimates. In this case, only descriptive statistics or listings will be provided.

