12.5.2.2.2. DOCR, DOCRh, DOR, and DOCRI

Among subjects who achieved CR, DOCR will be calculated as the date of the first occurrence of CR to the date of first documented disease relapse, or death.

Among subjects who achieved CR or CRh, DOCRh will be calculated as the date of the first occurrence of CR or CRh to the date of first documented disease relapse or death.

Among subjects who achieved CR, CRi (including CRp), PR, and MLFS, DOR will be calculated as the date of the first response to the date of first documented disease relapse, disease progression, or death.

Among subjects who achieved CR or CRi (including CRp), DOCRI will be calculated as the date of the first occurrence of CR or CRi (including CRp) to the date of the first documented relapse or death.

Kaplan-Meier methods will be used to estimate DOCR, DOCRh, DOR, and DOCRi; subjects without relapse, disease progression, or death, as appropriate, at the time of analysis will be censored at the last response assessment date. Kaplan-Meier estimates of DOCR, DOCRh, DOR, and DOCRi will be presented by treatment arm, including estimates of the median and other quantiles, as well as individual time points (eg, 3-, 6-, and 12-month rates).

Subjects will be censored for DOCR, DOCRh, DOR, or DOCRi at the time of the start of subsequent anticancer therapy, should it occur prior to any DOCR, DOCRh, DOR, or DOCRi event, as appropriate. Detailed censoring rules will be included in the SAP. Kaplan-Meier estimates of DOCR, DOCRh, DOR, and DOCRi will be presented by treatment arm, including estimates of the median and other quantiles, as well as individual time points (eg, 3-, 6-, and 12-month rates).

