7.7.2.3. Complete Remission Plus Complete Remission with Partial Hematologic Recovery

The CR+CRh rate is defined as the proportion of subjects who achieved a CR or CRh. CRh is defined as a CR with partial recovery of peripheral blood counts [$<5\%$ bone marrow blasts, ANC $>0.5 \times 10^9/L$ (500/ μ L), and platelets $>50 \times 10^9/L$ (50,000/ μ L)].

Since CRh is not part of modified IWG criteria, it will be derived by the Sponsor based on the following rules, for each individual assessment which is not CR.

- Bone marrow blast $<5\%$, and
- Closest ANC within ± 8 days $>0.5 \times 10^9/L$, and
- Closest platelet counts within ± 8 days $>50 \times 10^9/L$, and
- Assume negative if Auer rod is not reported, and
- Assume negative if extramedullary disease is not reported

For bone marrow blasts, bone marrow aspirate will be used as the primary source. If a bone marrow aspirate assessment is not available, a bone marrow biopsy assessment will be used.

For ANC or platelet count, if there are 2 values which have the same distance to the bone marrow assessment date (eg, one is 1 day prior and the other is 1 day after), the value from the earlier assessment date will be used.

If the primary analyses of EFS, CR and OS are statistically significant, a CMH test stratified by the randomization stratification factors will be used to compare the CR+CRh rate between the 2 treatment arms at 1-sided 2.5% level of significance. The odds ratio and its associated 95% CI will be presented.

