7.7.3.3. TTCR, TTCRh, TTR, and TTCRI

TTCR is defined, for subjects who achieve CR, as the time from randomization to the first occurrence of CR.

$$\text{TTCR (months)} = (\text{first date of CR} - \text{date of randomization} + 1) / 30.4375$$

TTCRh is defined, for subjects who achieve CR or CRh, as the time from randomization to the first occurrence of CR or CRh.

$$\text{TTCRh (months)} = (\text{first date of CR or CRh} - \text{date of randomization} + 1) / 30.4375$$

TTR is defined, for subjects who achieve CR, CRi (including CRp), PR, or MLFS, as the time from randomization to the first response.

$$\text{TTR (months)} = (\text{first date of response} - \text{date of randomization} + 1) / 30.4375$$

TTCRI is defined, for subjects who achieve CR or CRi (including CRp), as the time from randomization to the first occurrence of CR or CRi (including CRp).

$$\text{TTCRI (months)} = (\text{first date of CR or CRi} - \text{date of randomization} + 1) / 30.4375$$

TTCR, TTCRh, TTR, and TTCRI will be summarized by treatment arm using descriptive statistics.

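### The SAP formula for DOCRh omits CR from the start date, contradicting its own definition; read literally, some CR responders get no start date or a late one

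*SAP*

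**What the plan says.** SAP 7.7.3.2 states the rule in words: "DOCRh is defined, for subjects who achieved CR or CRh, as the time from the first occurrence of CR or CRh to confirmed relapse". A death from any cause also counts as the event. The line below turns this into a calculation in months. It takes the event or censoring date, subtracts the "first date of CRh", adds 1 and divides by 30.4375.

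Other places bear on the same start date:

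- Protocol 12.5.2.2.2: "DOCRh will be calculated as the date of the first occurrence of CR or CRh to the date of first documented disease relapse or death".
- SAP 7.7.3.2, DOCRi formula (the same construction for CR and CRi): the start is the "first date of CR or CRi".
- SAP 7.7.3.3, TTCRh formula (time from randomization to the same response): the end point is the "first date of CR or CRh".
- SAP 7.7.2.3: the sponsor derives CRh "for each individual assessment which is not CR".

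The endpoint lists in protocol 6.2.2 and SAP 3.2.2 both place DOCRh among subjects who reached either CR or CRh. SAP 7.7.3.2 plans Kaplan-Meier estimates by arm, with medians and rates from 3 to 36 months.

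**The concern.** Of the formulas in SAP 7.7.3.2 and 7.7.3.3 that combine CR with a lesser response by name, only the DOCRh formula leaves CR out of its date. CRh cannot be read as shorthand for either response, because SAP 7.7.2.3 assigns it only at assessments that did not qualify as CR. A CR date is never a CRh date.

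If the formula were programmed as printed, some complete responders would drop out of the Kaplan-Meier estimate or enter it with a shortened duration. In those subjects DOCRh would also disagree with TTCRh. Time to response would stop at the CR date, while duration would start later or not at all.

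The protocol wording does not automatically settle the conflict. Protocol 12.1 leaves full analysis detail to the SAP, and SAP section 2 says that the SAP may change what the protocol outlines.

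**Working it through.** **Inputs.** The SAP 6.2.1 power table assumes CR rates of 20% (control) and 40% (AG-120), and CR+CRh rates of 25% and 45%, with 200 subjects randomized 1:1 and a one-sided 2.5% level. Protocol 5.2.3.2 gives Phase 1b rates of 60.9% CR and 69.6% CR+CRh in 23 subjects. SAP 7.7.1.1.1 sets assessments at Weeks 9, 17, 25, 33, 41, 53 and every 24 weeks thereafter.

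**Check on the source of the rates.** The documents state no figure for DOCRh itself, so I checked the power figures that rest on these rates. A pooled-variance normal approximation with 100 per arm gives 84.8% for CR+CRh (stated 84%), 87.6% for CR (stated 86%) and 82.2% for objective response (stated 81%). All agree within 2 points, so the rates are read correctly.

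**What the printed formula does in each case.**

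| Response path | Start under the definition | Start under the printed formula |
|---|---|---|
| CRh only | first CRh | first CRh (correct) |
| CRh, then CR | first CRh | first CRh (correct) |
| CR, never CRh | first CR | none |
| CR, then CRh | first CR | first CRh (late) |

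**Length of the delay in the last row.** It depends on the gap between visits: 8 × 7/30.4375 = 1.8 months for an 8-week gap, 12 × 7/30.4375 = 2.8 months for the gap from Week 41 to Week 53, and 24 × 7/30.4375 = 5.5 months for a later gap.

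**Share of the DOCRh population that are CR responders.**

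- Control: 20/25 = 80%, so CRh-only is 20%.
- AG-120: 40/45 = 88.9%, so CRh-only is 11.1%.
- Both arms: 60/70 = 85.7%.
- Phase 1b: the percentages correspond to 14 and 16 of 23, and 14/16 = 87.5%.

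**Share affected.** Let f be the proportion of CR responders whose first CRh came before their first CR. The documents do not give f, so it is varied here as an assumption. The affected share is (1 − f) × CR share:

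| f | Control | AG-120 | Affected per 100 randomized (control / AG-120) |
|---|---|---|---|
| 0 | 80% | 89% | 20 / 40 |
| 0.25 | 60% | 67% | 15 / 30 |
| 0.50 | 40% | 44% | 10 / 20 |
| 0.75 | 20% | 22% | 5 / 10 |

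The affected share exceeds one half only if f is below 1 − 0.5/0.80 = 37.5% in control, 1 − 0.5/0.889 = 43.75% in the AG-120 arm, or 1 − 0.5/0.857 = 41.7% overall.

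**After correction.** Every subject with CR or CRh has a defined start date that agrees with the worded definition, the protocol and TTCRh. No sample size, power or alpha figure changes.

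**The case against.** The strongest reply is that the intended rule is beyond doubt. It is worded in the protocol and again immediately above the formula, the SAP abbreviation list expands DOCRh as the duration of CR+CRh, and the TTCRh formula shows the right date. Nothing suggests that a CRh-only start was chosen; this looks like two omitted words. A literal program would also leave missing start dates, and the DOCRh count would fall short of the CR+CRh responder count, so the error should surface. The endpoint carries little inferential weight: protocol 12.5 gives it no alpha control, and SAP 7.7.3.2 plans no between-arm test.

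All of that stands as a limit on importance, but it does not remove the contradiction. The count check would catch only subjects with no CRh date. A subject with CR and then CRh still has a date and is counted, so that error would pass unnoticed. The protocol's own abbreviation list expands DOCRh without the CR component, which gives a programmer no help.

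A reader might go further and infer three things that the documents do not support:

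- *Most of the covered subjects are misdated.* This requires f to be below about 38% to 44%, and f is unknown.
- *The resulting curve mainly describes weaker responders.* The subjects who keep a date include CRh-then-CR and CR-then-CRh subjects, in unknown number.
- *The loss differs by arm.* At a common f the gap is at most 8.9 points. With f = 0 in control and f = 0.10 in the AG-120 arm it vanishes (0.90 × 88.9% = 80%), and with other values it reverses.

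**Conclusion.** The formula is wrong as written, and this is certain from the text alone. It contradicts the definition it is meant to implement, the protocol and its sibling formulas. Read literally, it leaves CR responders without CRh undated and dates CR-then-CRh subjects late.

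The size is bounded rather than known. On the plan's assumed rates, at most 80% of the control and 89% of the AG-120 DOCRh population would be affected, falling in proportion to the share of CR responders who passed through CRh first. The split between missing and late starts is also not given.

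The consequence is confined to one descriptively summarized additional secondary endpoint. EFS, the key secondary tests (CR, OS, CR+CRh and ORR) and all power figures are untouched. It is best treated as a drafting inconsistency to be corrected before programming, so that no undocumented choice between formula and definition is left until after unblinding.

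**What to change.** In SAP 7.7.3.2, replace the DOCRh formula with:

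DOCRh (months) = (date of event or censoring − first date of CR or CRh + 1)/30.4375.

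This adds two words and needs no new data. A useful programming check is that the DOCRh start date equals the TTCRh response date for every subject, and that the number of subjects in the DOCRh analysis equals the number of CR+CRh responders.

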7.7.3.3. TTCR, TTCRh, TTR, and TTCRI

TTCR is defined, for subjects who achieve CR, as the time from randomization to the first occurrence of CR.

$$\text{TTCR (months)} = (\text{first date of CR} - \text{date of randomization} + 1) / 30.4375$$

TTCRh is defined, for subjects who achieve CR or CRh, as the time from randomization to the first occurrence of CR or CRh.

$$\text{TTCRh (months)} = (\text{first date of CR or CRh} - \text{date of randomization} + 1) / 30.4375$$

TTR is defined, for subjects who achieve CR, CRi (including CRp), PR, or MLFS, as the time from randomization to the first response.

$$\text{TTR (months)} = (\text{first date of response} - \text{date of randomization} + 1) / 30.4375$$

TTCRI is defined, for subjects who achieve CR or CRi (including CRp), as the time from randomization to the first occurrence of CR or CRi (including CRp).

$$\text{TTCRI (months)} = (\text{first date of CR or CRi} - \text{date of randomization} + 1) / 30.4375$$

TTCR, TTCRh, TTR, and TTCRI will be summarized by treatment arm using descriptive statistics.

7.7.3.4. Quality of Life Assessments

Summaries of QoL data will be presented by treatment arm based on the FAS.

7.7.3.4.1. Descriptions of Questionnaires

7.7.3.4.1.1. European Organization of Research and Treatment of Cancer – Quality of Life Questionnaire – Core Questionnaire (EORTC-QLQ-C30)

The EORTC QLQ-C30 is a validated and reliable self-reported measure of QoL for subjects with cancer who are receiving cancer treatment. The QLQ-C30 contains 30 items in total and each item is a 4-point or 7-point Likert scale. These 30 items can be categorized into 1 global health status/HRQOL scale, 5 functional scales, 3 symptom scales, and 6 single item scales. Each of the multi-item scales includes a different set of items. No item occurs in more than one scale:

- 1 global health status scale (2 items)

- 5 functional scales: physical function (5 items), role function (2 items), emotional function (4 items), cognitive function (2 items), social function (2 items)
- 3 symptom scales: fatigue (3 items), nausea and vomiting (2 items), pain (2 items)
- 6 single-item scales relating to dyspnea, insomnia, appetite loss, constipation, diarrhea, and financial difficulties

7.7.3.4.1.2. EuroQoL EQ-5D-5L (EQ-5D-5L)

The EuroQoL EQ-5D-5L is a widely used standardized measure of health status that provides a descriptive profile and single index value to appraise respondents' health status. The measure was designed for both clinical and economic appraisal and has been validated in numerous clinical populations. The EQ-5D-5L is comprised of five single-item dimensions: mobility, self-care, usual activities, pain/discomfort and anxiety/depression. These dimensions are measured on a 5-level scale: “No problems”, “Slight problems”, “Moderate problems”, “Severe problems”, and “Extreme problems.”

EQ-5D-5L responses can also be converted into summary index values, using established population-based value sets. Index values reflect general population valuations of a given health state, as constituted by the EQ-5D-5L responses, where a score of 0 is equivalent to being dead and 1 is equivalent to perfect health.

The EQ-5D-5L also contains a visual analog scale (VAS) to assess the subject's overall health on a scale of 0 (“The worse health you can imagine”) to 100 (“The best health you can imagine”).

7.7.3.4.2. Statistical Analyses

Scores for the EORTC QLQ-C30 and EQ-5D-5L will be summarized at each visit where data are available.

Completion rates will be calculated for each instrument at each assessment visit as the proportion of subjects alive at the assessment visit with a completed instrument.

7.7.3.4.2.1. EORTC-QLQ-C30

Each scale will be transformed into a 0-100 score following EORTC guidelines:

- Estimate the average of the items that contribute to the scale; this is the raw scale score
- Use a linear transformation to standardize the raw scale score, so that it ranges from 0 to 100. $\text{Scale score} = (\text{raw score} - 1) / \text{range} * 100$, where range is the difference between the maximum and minimum possible value of the raw score from each item

Transformed scores for each scale, and the absolute and percent changes from baseline will be summarized by treatment arm at each visit.

Mixed models will also be applied in the analysis of the EORTC QLQ-C30. All available data for each subject will be used in the analysis. The mixed model on the change from

baseline across visits for all scales will be performed with baseline score, treatment arm, time, randomization stratification factors and an interaction between treatment arm and time as fixed effect, and subject as random effects. All parameter estimates will be obtained using restricted maximum likelihood. The unstructured covariance structure will be used to define covariance between random effects (using option “Type=UN” as a part of the RANDOM statement in PROC MIXED). For the degrees-of-freedom calculations the Kenward and Roger algorithm will be used (using option “ddfm=kr” as a part of the MODEL statement in PROC MIXED). The least square means and 95% CI will be summarized and graphically presented by treatment arm over time.

7.7.3.4.2.2. EQ-5D-5L

The first response is coded as a 1 (indicating no problems), the second response is coded as a 2 (indicating slight problems), the third response is coded as a 3 (indicating moderate problems), the fourth response is coded as a 4 (indicating severe problems), the fifth response is coded as a 5 (indicating extreme problems). Ambiguous responses (eg, more than 1 response in a dimension) are treated as missing values.

For each dimension, the number and percentage of subjects with no problems, slight problems, moderate problems, severe problems and extreme problems will be summarized by treatment arm at each visit.

EQ-5D-5L responses will also be converted into index values using a US value set. Summary statistics for index scores and the absolute and percent change from baseline will be reported by treatment arm at each visit.

The EQ-5D-5L also contains a utility scale of health state (VAS) ranging between 0 (worst health) and 100 (best health). Summary statistics for VAS scores and the absolute and percent change from baseline will be reported by treatment arm at each visit.

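### The SAP scores all 15 QLQ-C30 scales with one increasing formula and states no item coding or score direction, so the direction of the five functional scales is not fixed; percent change is also undefined at a baseline of 0

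*SAP*

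**What the plan says.** SAP 7.7.3.4.1.1 describes the instrument: "The QLQ-C30 contains 30 items in total and each item is a 4-point or 7-point Likert scale". It sorts the items into one global scale, three symptom scales, six single items and "5 functional scales: physical function (5 items), role function (2 items), emotional function (4 items), cognitive function (2 items), social function (2 items").

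SAP 7.7.3.4.2.1 then sets the scoring. The scope is universal and cites an outside standard: "Each scale will be transformed into a 0-100 score following EORTC guidelines". The raw score comes first: "Estimate the average of the items that contribute to the scale; this is the raw scale score". The second step is "Use a linear transformation to standardize the raw scale score, so that it ranges from 0 to 100", by (raw score − 1)/range × 100, "where range is the difference between the maximum and minimum possible value of the raw score from each item". No second formula is given for any type of scale.

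Two analyses use the scores. One is descriptive: "Transformed scores for each scale, and the absolute and percent changes from baseline will be summarized by treatment arm at each visit". The other is a mixed model for change from "baseline across visits for all scales will be performed with baseline score, treatment arm, time, randomization stratification factors" and a treatment-by-time interaction. Its least-squares means are tabulated and plotted by arm.

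Neither document says what response codes 1 and 4 (or 1 and 7) stand for, or whether a higher score on a QLQ-C30 scale is better or worse. Protocol 10.8.3 and 12.5.2.2.5 give no scoring formula. For EQ-5D-5L, by contrast, the SAP states the meaning of codes 1 to 5 and the direction of the VAS.

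**The concern.** The formula preserves the order of the item codes. It gives a score in which higher is better only where a higher code is the better answer. The SAP applies it alike to scales named for function and to scales named for symptoms, without saying whether their items are coded in the same direction. If they are, and a higher code means more trouble, a rise in a scale labelled physical function would mean that function had worsened.

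What is at stake is how a listed secondary endpoint is read (change from baseline in QoL: Protocol 6.2.2, SAP 3.2.2). With no direction stated, a reader of the tables and plots cannot tell benefit from harm on five of the 15 scales. Two programmers could produce mirror-image results, one using the written formula and the other the cited guidelines, and both could claim to have followed the SAP.

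The percent change is a separate matter. The formula places the best or worst attainable state at exactly 0, and the SAP plans to divide by the baseline score.

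**Working it through.** **Inputs from the SAP.** Raw score = mean of the items. Range = 3 for 4-point items and 6 for 7-point items. Scales: 1 + 5 + 3 + 6 = 15. Functional items: 5 + 2 + 4 + 2 + 2 = 15 of the 30.

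**Input not in the documents.** The direction of the functional item codes. Both possibilities are carried: (A) a higher code means more difficulty; (B) a higher code means better function.

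**1. The stated 0 to 100 range reproduces.** With range 3, codes 1, 2, 3, 4 give 0, 33.3, 66.7, 100. With range 6, codes 1 to 7 give 0, 16.7, 33.3, 50, 66.7, 83.3, 100. The formula is increasing throughout.

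**2. Comparison with a reversed form.** Let S = (raw − 1)/range × 100 and R = [1 − (raw − 1)/range] × 100, so S = 100 − R.

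| Raw (4-point items) | S, as written | R, reversed |
|---|---|---|
| 1 | 0 | 100 |
| 2 | 33.3 | 66.7 |
| 3 | 66.7 | 33.3 |
| 4 | 100 | 0 |

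Under A, S gives full function 0 and maximal limitation 100, and R gives the direction that the scale names suggest. Under B, S already gives that direction and R would be wrong.

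**3. Effect on absolute change.** A change in S is minus the change in R. Take physical function (five items) moving from raw 2.4 to 1.8, an improvement under A:
- As written: 46.7 to 26.7, a change of −20.0.
- Reversed: 53.3 to 73.3, a change of +20.0.

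**4. Effect on the mixed model.** Write change = a + βb + τ·arm + other terms, with b the baseline score. Put change′ = −change and b′ = 100 − b. Then change′ = (−a − 100β) + βb′ − τ·arm − other terms. The baseline slope is unchanged, and the treatment coefficient changes sign but keeps its standard error. A fit to invented data agrees (100 per arm, four visits, random subject intercept, stratification factors omitted). The treatment coefficient at the first of those visits is −9.59 (95% CI −13.18 to −6.00) as written and +9.59 (6.00 to 13.18) reversed, with SE 1.83 and the same p-value both ways. The figures show only the symmetry and do not predict this trial.

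**5. Percent change, under any coding.** This does not simply change sign.

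| Raw, baseline to later | S: scores, percent change | R: scores, percent change |
|---|---|---|
| 1.0 to 1.4 | 0 to 13.3, undefined | 100 to 86.7, −13.3% |
| 1.2 to 1.6 | 6.7 to 20.0, +200% | 93.3 to 80.0, −14.3% |
| 2.4 to 1.8 | 46.7 to 26.7, −42.9% | 53.3 to 73.3, +37.5% |

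The first two rows are the same absolute move of 13.3 points. With S the denominator is zero at raw 1; with R it is zero at raw 4. Reversal moves the undefined cases to the other end of the scale and does not remove them.

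**The case against.** The strongest reply is that the SAP says it follows EORTC guidelines. If those guidelines score functional scales separately, the written formula is an incomplete summary of the adopted standard, and a program built from the standard would give the intended direction. This is a fair limit on the point. A reader might infer that functional results will be reported with the wrong sign, so that better functioning on AG-120 would appear as a loss. The documents do not support that. They give neither the item coding nor the content of the guidelines, and the formula alone reverses nothing. That reading also presupposes a result for one arm, whereas any reversal would apply equally to both. What stands is that the written rule covers every scale. If the guidelines differ from it, the SAP conflicts with itself; if they do not, the direction is still unstated.

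Second, the planned model output is least-squares means by arm, and no QoL arm difference or p-value is named. If a difference were derived, its size and precision would not change. This is correct: for absolute changes the problem is one of direction and labelling, not of lost information.

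Third, division by a zero baseline affects any score that can be 0, including the symptom scales, and the SAP also plans percent change for the EQ-5D-5L index and VAS. That is true, and it is why reversing the functional scales does not cure it. It does not justify keeping the summary for QLQ-C30, where 0 is an attainable end of every scale.

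Fourth, the impact is small. QoL lies outside the fixed sequence of EFS, CR, OS, CR+CRh and ORR, and Protocol 12.5 applies no alpha control to other analyses. This stands in full.

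**Conclusion.** The point holds conditionally on direction and unconditionally on percent change.

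- **Direction.** The SAP states one increasing formula for all 15 scales, with no coding and no direction. If higher functional codes mean more difficulty and the formula is applied as written, five scales run opposite to their names, and every absolute change or arm difference on them has the opposite sign with the same size, SE and p-value. They would also run opposite to global health status, provided that higher codes on its two items mean better health, which the documents do not state either. Under the opposite functional coding nothing is reversed. The supportable conclusion is that the direction is not pre-specified and that the text may conflict with the standard it cites. A wrong sign in the report is a possibility, not an established outcome.
- **Percent change.** Undefined at a baseline score of 0 and unstable just above it (+200% for a 13.3-point move from 6.7). No coding assumption is needed.

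The consequence is confined to an additional secondary endpoint. EFS, the key secondary endpoints and the EQ-5D-5L scores are unaffected. The correction should be made because the ambiguity is real and nearly free to remove before scoring is programmed.

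**What to change.** In SAP 7.7.3.4.2.1:

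1. State the meaning of the lowest and highest response code for the functional, symptom, single-item and global items.
2. Give the formula by scale type. If higher functional codes mean more difficulty, use [1 − (raw score − 1)/range] × 100 for the five functional scales and keep (raw score − 1)/range × 100 for the global, symptom and single-item scales. If the coding is the other way, keep the present formula for the functional scales and say so.
3. State for each scale type whether a higher score is better or worse, and repeat this on the tables and plots.
4. Check the result against the cited EORTC guidelines and name the edition of the scoring manual, so that formula and citation agree.
5. Drop percent change from baseline for QLQ-C30. Keep absolute change, which is already planned and is what the mixed model uses.

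The cost is a few lines of SAP text and a check of the scoring program. No new data are needed, and sample size, alpha and the primary and key secondary analyses do not change.
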